In the case of treatment with a fixed dose, the patient is usually treated with a therapeutic dose of I-131 without performing a preliminary biodistribution study. However, in the case of treatment with the maximum safe dose of I-131 based on dosimetry, it is necessary to give an initial small dose of radioiodine, usually I-131, to measure the biodistribution of radioiodine and in turn to calculate the maximum dose that the patient can safely tolerate. The dilemma is that there is significant, but controversial, evidence that the initial small dose of I-131 may stun the thyroid metastases and decrease the uptake of the subsequent therapeutic dose of I-131, thus defeating the purpose of dosimetrically determining the maximum safe dose (4,10-20).

The radioisotope of iodine, I-123, is a pure gamma emitter and is thought to be less likely to cause stunning than I-131. However, there are some reports that even I-123 can cause stunning (21-24).

If it is demonstrated that I-123 does not cause significant stunning, a follow-up separately funded prospective study can be designed to determine whether a dosimetrically determined dose of I-131 is superior to a fixed dose. If an individually calculated maximum dose is determined to be superior, it would suggest that the dosimetric approach, which is currently used in only a

small minority of patients, should be offered to all patients. This would represent a major advance in the treatment of patients with metastatic differentiated thyroid cancer. Alternatively, if a dosimetrically determined dose of I-131 is not superior to a fixed dose, all patients can be treated with the simpler less costly fixed dose regimen.

III. Preliminary Studies/Progress Report: N/A

IV. Research Methods

A. Outcome Measure(s): Difference in uptake of I-123 in the thyroid remnant in the neck in the two imaging studies. Greater than a 20% decrease from the first to second study will indicate evidence of stunning.

B. Description of Population to be Enrolled:

Inclusion criteria:

1. Patient must be 21-years-old or greater.
2. Patient must be status post near total thyroidectomy for differentiated thyroid cancer without known distant metastases and who are planning to undergo routine remnant thyroid tissue ablation with I-131.
3. Patients must qualify for thyroid ablation with I-131.

Exclusion criteria:

1. Women who are pregnant or breastfeeding.
2. Prior bovine TSH use.
3. Known metastatic thyroid cancer.

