4. History of cardiovascular disease that may adversely affect patient participation at the discretion of the primary investigator.
5. Patients on hemodialysis.
6. Patients with acute serious illnesses at the discretion of the primary investigator.

C. Study Design and Research Methods: The proposed research will be the first study to perform test-retest studies in a group of patients to answer the long standing and fundamental question of whether diagnostic doses of I-123 cause stunning. Ten patients will be studied. If the patient elects to pursue participation in the study, the consent form will be explained to the patient

If the patient consents, the patient will undergo two I-123 whole body imaging studies prior to the I-131 thyroid remnant ablation.

Figure 1. General Scheme of Investigational Plan

The current standard of care is indicated in the solid black boxes and the additional research component is the dashed boxes.

[figure not shown]
[figure not shown]

Figure 2. Timing of standard of care and research interventions for the study population.

Patient Preparation

Participants will be placed on a low iodine diet for 1 week before the dosimetry study and continue on this diet until 24 hours after the therapeutic dose of ^{131}I .

Patient is prepared for the study by receiving an intramuscular injection of rhTSH (Thyrogen). The patients are prepared for receiving radioiodine by receiving an intramuscular injection of rhTSH (Thyrogen) on days 1, 2, 8, 9, 15 and 16 in order to raise the blood level of TSH and maximally stimulate the residual thyroid tissue to take up iodine (25-27). The Thyrogen received on days 1, 2, 8 and 9 will be provided free of charge by Genzyme. The subject's vital signs will be monitored before and after each Thyrogen injection. The Thyrogen injection will be withheld if vital signs show significant alterations from the patient's baseline.

Female patients of reproductive age who have not undergone a hysterectomy will undergo serum pregnancy tests on days 3 and 17 prior to administration of radioiodine.

All patients will have blood samples taken on days 3, 10, and 17 in the morning, to document that rhTSH was given and that there was a rise in thyroglobulin level (TSH action on thyroid cells) prior to administration of radioiodine.

Diagnostic imaging with I-123

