On days 3 and 10 the patient is given 3 mCi of ^{123}I orally in the morning. The participant will be asked to fast at least 4 hours before and 1 hour after the I-123 oral dose to control for interference with I-123 uptake.

Imaging with gamma camera from the top of the head to the thighs is performed on days 4 and 11.

In each of the I-123 whole body diagnostic imaging studies, one done for research purposes and the other as routine care, a region of interest will be placed over the I-123 uptake in the residual thyroid tissue and the number of counts will be recorded (28). Less than a 20% decrease in counts from the first to the second study will be considered no significant stunning (29). The Null hypothesis is that there will be less than a 20% decrease in I-123 in the thyroid remnant from the first to the second study.

In order to more accurately measure I-123 uptake in the residual thyroid tissue from the I-123 whole body diagnostic image, an I-123 standard will be placed in the field of imaging at the time of image acquisition. Use of I-123 standard is common practice for calibrating I-123 activity in the body. By using an I-123 standard, in addition to recording the number of counts in the residual thyroid tissue and comparing the count differences between the first and second study, percent uptake of I-123 in the residual thyroid tissue can be calculated for each study and compared. Less than a 20% decrease in percent uptake of I-123 in the residual thyroid tissue will be considered no significant stunning and provide additional supportive data to measuring counts in the residual thyroid tissue.

If thyroid cancer metastases are incidentally discovered in the patient with no known metastases, the patient will be removed from the study and referred back to Endocrinology.

Thyroid tissue ablation with I-131

On day 17, the patient is given a fixed therapeutic dose of ^{131}I determined by the endocrinologist and nuclear medicine physician (range 30-100 mCi ^{131}I).

Post-treatment imaging evaluation

Approximately 7 to 10 days after therapeutic dose of radioiodine (day 23-26), patient returns for routine, standard of care post ^{131}I treatment imaging.

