F. Data Analysis Plan: The primary endpoint will be measurement of thyroid remnant activity at 24 hours. We predict there will be less than a 20% reduction in the amount of I-123 in the thyroid remnant when the results of the second administered dose of I-123 is compared to the results from the first dose of I-123. The data will be analyzed statistically by the t-test and by the sign test. While we plan to study only 10 participants, this should be a sufficient number to determine whether there is any evidence of stunning by the sign test and, if there is stunning, whether there is more than a 20% stunning effect by the t-test. This is a pilot study, but it is likely to give results that are sufficiently definitive that it will not need to be repeated with larger numbers of participants. In addition, this is an internally funded research project that is intended to generate preliminary data to be

used in a larger NIH grant proposal that will compare fixed versus dosimetrically determined I-131 doses for treatment of patients with differentiated thyroid cancer with distant metastases.

G. Monitoring and Oversight

The sponsor investigator will be responsible for monitoring the trial per the trial monitoring plan, in addition to overseeing the safety and efficacy of the trial including any specimens collected, executing the data and safety monitoring (DSM) plan, and complying with all reporting requirements to local and federal authorities. This oversight will be accomplished through additional oversight from the Data and Safety Monitoring Committee (DSMC) at the University of Colorado Cancer Center (CU Cancer Center). The DSMC is responsible for ensuring data quality and study participant safety for all clinical studies at the CU Cancer Center, which is the coordinating institution of this trial. A summary of the DSMC's activities is as follows:

- Conduct of internal audits
- Ongoing review of all serious adverse events (SAEs), unanticipated problems (UAPs) and reportable adverse events (AEs)
- Has the authority to close and/or suspend trials for safety or trial conduct issues
- May submit recommendations for corrective actions to the CU Cancer Center's Executive Committee

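### Section IV.F tests for any stunning with a sign test, which at an assumed 5% level needs 9 falls in 10 pairs and can miss a group fall that a signed-rank or paired t-test on the same continuous data would show

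*Combined protocol and SAP*

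**What the plan says.** Section IV.F (Data Analysis Plan) names two tests without condition: "The data will be analyzed statistically by the t-test and by the sign test". The next sentence, which defends the sample size, gives each a role. The ten participants are to determine "whether there is any evidence of stunning by the sign test and, if there is stunning, whether there is more than a 20" per cent effect by the t-test. The sign test thus takes the question of any stunning, and the t-test takes the 20% question.

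The data are continuous. In Section IV.C, under the heading on diagnostic imaging, "a region of interest will be placed over the I-123 uptake in the residual thyroid tissue and the number of counts will be recorded" for both studies, and percent uptake is calculated with the help of an I-123 standard. The sample size is fixed: "Ten patients will be studied".

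Section IV.A sets the outcome criterion separately: "Greater than a 20% decrease from the first to second study will indicate evidence of stunning". Section IV.C writes a null hypothesis around the same 20% figure.

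The documents do not state a significance level, sidedness, power, the SD of the within-patient change, or how ties are handled. Section III (Preliminary Studies) is marked not applicable.

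**The concern.** A sign test uses only whether each patient's value went up or down. A fall of 2% and a fall of 50% count the same, so the magnitudes that the trial takes care to measure drop out of the test assigned to the first question. With ten pairs the test is also coarse. No attainable p-value lies between the one for 8 falls and the one for 9, so two small rises are enough to make it non-significant, however large the other eight falls are.

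The protocol expects its results to be definitive enough not to need repeating, and Sections IV.F and IV.H look ahead to a larger study. If a real group fall below or near 20% went undetected, that study would start from a mistaken premise. The loss is avoidable, because the same ten pairs support a more sensitive test.

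The wording of the second role raises a further question: whether the 20% comparison is meant to be run only after a positive sign test.

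**Working it through.** **Inputs.** From the documents: 10 pairs (Section IV.C), a 20% threshold (Sections IV.A and IV.C), a sign test for any stunning and a t-test for the 20% question (Section IV.F). Assumed: a 5% level, no ties, and a normally distributed log(scan 2/scan 1) with SD 0.10 to 0.40. The plan gives no calculation behind ten participants, so there is no power figure to reproduce.

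**Step 1. Sign test cut-off.** Under no change, the number of falls is Binomial(10, 0.5).
- 8 or more falls: (45 + 10 + 1)/1024 = 0.0547 one-sided, 0.109 two-sided.
- 9 or more falls: (10 + 1)/1024 = 0.0107 one-sided, 0.0215 two-sided.

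So 9 of 10 are needed at 5%, whichever sidedness is used, and the actual two-sided level is 2.1%. The exact two-sided signed-rank test at n = 10 runs at 2 × 25/1024 = 4.9%. If patients are removed, as Section IV.C allows, the two-sided requirement becomes 8 of 9 (p = 0.039) or 8 of 8 (p = 0.008).

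**Step 2. Power for a true 20% fall, two-sided 5%.** The shift on the log scale is −ln(0.80) = 0.223.
- Sign test: the probability that one patient falls is p = Φ(0.223/SD), and power is 10p⁹(1 − p) + p¹⁰. At SD 0.25, p = Φ(0.893) = 0.814 and power is 0.419.
- Paired t-test: noncentral t on 9 df with noncentrality √10 × 0.223/SD.
- Signed-rank: exact critical value (rank sum of 47 or more out of 55), power by simulation.
- Last column: the paired t-test held to the sign test's own 2.15% level.

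| SD of log ratio | Sign | Signed-rank | Paired t | Paired t at 2.15% |
|---|---|---|---|---|
| 0.10 | 0.99 | 1.00 | 1.00 | 1.00 |
| 0.20 | 0.61 | 0.86 | 0.88 | 0.76 |
| 0.25 | 0.42 | 0.69 | 0.71 | 0.54 |
| 0.30 | 0.30 | 0.54 | 0.555 | 0.39 |
| 0.40 | 0.17 | 0.34 | 0.35 | 0.22 |

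For SD 0.20 to 0.30, the t-test is significant and the sign test is not in about 27 to 30% of simulated trials. The reverse happens in about 1%.

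**Step 3. Heavy tails.** With changes in percentage points following a t distribution on 2 df (shift 20, scale 20), power is 0.34 for the sign test, 0.41 for the t-test and 0.46 for the signed-rank test. The gap narrows but keeps its direction.

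**Step 4. Illustration.** Take falls of 30, 28, 25, 22, 20, 18, 15 and 12% and rises of 2 and 4%.
- Mean fall 16.4, SD 11.63, t = 16.4/(11.63/√10) = 4.46, p = 0.002.
- The rises hold ranks 1 and 2, so the smaller rank sum is 3 and the signed-rank p = 2 × 5/1024 = 0.010.
- Sign test, 8 of 10: p = 0.109.

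**Step 5. If the 20% t-test were run only after a significant sign test.** The cost is the probability that the t-test against 20% is significant while the sign test is not. With a one-sided 5% t-test it is about 0.8 points at a true fall of 34% and SD 0.25. It is about 4.3 points at a 35% fall and 5.8 at a 40% fall, both with SD 0.40. For SD 0.30 or less it is about 2 points at most.

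**The case against.** Four points on the other side carry weight.

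1. A reader might infer that the plan stops at a non-significant sign test and never compares the fall with 20%. The documents do not establish this. The sentence naming both tests is unconditional, and the conditional words sit in the following sentence, which argues for the sample size. No sequence or stopping rule is written. The conditional reading is possible, and it would cost the 20% comparison little.

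2. A reader might also infer that a large group fall, say a third, would be reported as no evidence of stunning. Section IV.A stands against that: it defines evidence of stunning as a fall of more than 20%, with no reference to the sign test. Nor do the documents suggest that the test was chosen to favour the expected answer. Section IV.F predicts a reduction of less than 20%, rather than none.

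3. Not all of the power gap comes from ignoring magnitude. Held to the sign test's own 2.15% level, the paired t-test leads by about 15, 12, 9 and 5 points at SD 0.20, 0.25, 0.30 and 0.40, against 27, 29, 26 and 18 points at the nominal 5%. About half or more of the gap is therefore discreteness. That explains the loss without removing it, since the alternatives use the 5% level more fully.

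4. The sign test is exact, needs no symmetry assumption and gives the same answer on the raw and log scales. Those are good reasons to keep it as a check. They are weaker reasons to make it the detector in a plan that already accepts a t-test.

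**Conclusion.** The point holds as a choice-of-test weakness that is cheap to mend. The sign test is valid, but it can miss a group fall that the same ten pairs would show under a signed-rank or paired t-test. For a true 20% fall and log-ratio SD of 0.20 to 0.40, it gives up roughly 17 to 27 points of power against the signed-rank test and 18 to 29 against the paired t-test. At SD 0.10 there is almost nothing to lose (0.99 against 1.00).

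These figures rest on a 5% level, ten untied pairs and normal log ratios, none of which the documents state, and on an assumed SD range. The requirement of 9 falls depends on the level: at one-sided 10%, 8 of 10 would do.

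The possible conditioning of the 20% test is an ambiguity of wording that costs under about 6 points. Changing the test does not make a negative result safe. At SD 0.30 to 0.40 the signed-rank test still misses a true 20% fall in 46 to 66% of trials.

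**What to change.** In Section IV.F, make the test for any fall the Wilcoxon signed-rank test, or the paired t-test, on the within-patient log ratio of scan 2 to scan 1. Name one of the two in advance, with its level and sidedness. Keep the sign test as a sensitivity analysis.

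Remove the opening conditional clause of "if there is stunning, whether there is more than a 20% stunning effect by the t-test", so that the comparison with 20% is always made and reported.

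Add that a non-significant result from any of these tests with ten patients will not be read as showing that stunning is absent.

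The cost is two or three sentences, with no new patients, scans or measurements. The one statistical price is that the signed-rank test assumes roughly symmetric log ratios; the retained sign test guards against a failure of that assumption.
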